### 4. OBJECTIVE(S)/SPECIFIC AIMS AND HYPOTHESES

- *A concise statement of the goal(s) of the current study.*
- *The rationale for and specific objectives of the study.*
- *The goals and the hypothesis to be tested should be stated.*

The current study aims to identify the required dose of a behavioral change technique (BCT) intervention to increase physical activity (PA) by an average of 2,000 steps per day among individuals on primary prevention statin therapy with elevated risk for cardiovascular disease (CVD). The study will utilize the modified time-to-event continual reassessment method (TiTE-CRM).

**Primary Aim:** Identify the MED of a multi-BCT intervention required to increase PA by an average of 2,000 steps per day between run-in and follow-up periods in at least 80% of participants.

**Secondary Aim 1:** To identify effect sizes for mediating MoAs of the BCT intervention on PA.

**Secondary Aim 2:** Identify additional benefits of the BCT intervention on statin adherence.

**Exploratory Aim:** Identify between-person heterogeneity in Treatment Response.

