## 9. STUDY TIMELINES

- *Describe the duration of an individuals participation in the study*
- *Describe the duration anticipated to enroll all study subjects*
- *The estimated date of study completion*

Participants in this research could remain on study for up to 14 weeks.

All participants will undergo a 2 week run-in period and will then be enrolled in cohorts of 3. The first cohort will be given BCT intervention with a duration of 5 weeks. Subsequent cohorts will be given a BCT intervention duration (from 1-week to 10-week) based on the updated MED estimate according to the modified TiTE-CRM model and data from the previously enrolled participants. The process will continue until we reach a total of 42 participants (14 cohorts) randomized to the intervention; see sample size justification below.

All participants will then undergo 2 weeks of observation. In summary, participation will be between 5– 14 weeks depending on BCT dose assignment.

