*Environmental context and resources* is defined as aspects of a person’s situation or environment that discourage or encourage the behavior. This MoA will be assessed using a checklist of 7 potential barriers to physical activity identified by Steinhart and colleagues [29] Barriers are coded on a 1 (Not often at all) to 5 (Very often) scale, and averaged to create a total score, with higher scores indicating that the listed barriers had greater effects on walking.

Following completion of the 2-week run-in period, participants will receive a variable duration BCT intervention, and the length of the intervention is determined by utilization of the modified TiTE-CRM design. During the BCT intervention, participants will receive 5 daily BCTs via text message. Content of the text message will be specific for each BCT (e.g. a Goal Setting text message will encourage participants to develop a walking goal for the day). Initially, 3 participants will be treated at a moderate dose level, which is five weeks of the multi-BCT intervention to increase PA. Based on the calculated MED for the first cohort, subsequent cohorts will be administered a longer or shorter dose of the intervention. The BCT dose for each cohort will be determined by the study statistician based on the proportion of individuals in the prior cohort exhibiting the target behavior (in this case, a 2,000 step per day increase between baseline and follow-up periods). As the MED involves comparing PA levels between the run-in and follow-up periods, participants will not be assigned to subsequent cohorts unless all of the participants in the prior cohort have completed some of the intervention period. The treatment response for the prior cohort will be used to guide the dose administered to the subsequent cohort using modified TiTE-CRM methodology.

Following the completion of the intervention, all cohorts will be assessed for a 2 week follow-up period. Follow-up consists of wearing the activity monitor continuously, and use of electronic pill bottle to assess adherence. No interventions will be delivered during this period. At the end of the study, participants will be asked to complete the same questionnaire completed during baseline and the intervention phase as well as a satisfaction survey regarding the BCT intervention. Participants will also be reminded/instructed to return their eCAP smart pill bottle to the study team via addressed packaging included in their study materials.

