## 12. STATISTICAL ANALYSIS

- *Describe how your data will be used to test the hypotheses.*
- *State clearly what variables will be tested and what statistical tests will be used.*
- *Include sample size calculations.*
- *If this is a pilot study, state which variables will be examined for hypothesis generation in later studies.*

Analysis for the Primary Aim: The minimum effective dose (MED) will be defined as the smallest BCT dose duration associated with a successful PA increase (defined as an average increase of 2,000 steps per day) between the 2-week run-in and 2-week follow-up periods in at least 80% of participants. The MED will be estimated based on the modified TiTE-CRM, which is an adaptive model-based, dose-finding design for estimating the maximum tolerated dose in pharmacologic agents. In this study, we will adapt the TiTE-CRM for the purpose of MED estimation. Briefly, the TiTE-CRM operates as follows during a study. Participants will be enrolled in cohorts of 3. The first cohort will be given a BCT intervention with a duration of 5 weeks. Subsequent cohorts will be given a BCT intervention duration (from 1-week to 10-week) based on the updated MED estimate according to the modified TiTE-CRM model and data from the previously enrolled participants. The process will continue until we reach a total of 42 participants (14 cohorts) randomized to the intervention. Once the study has completed enrollment, we will identify which dose of the BCT intervention (in weeks) is associated with  $\geq 80\%$  of participants achieving the goal of an average of 2,000 steps per day increase between the baseline and follow-up periods. Means and standard deviations of step scores for baseline versus behavioral change strategy treatment period will be visualized using a column graph. The statistical significance of differences will be adjusted for time interval. The effects of treatment on number of steps will be assessed using generalized linear mixed models (GLMM). This model will account for possible autocorrelation and linear trends between steps across time.

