The dose-efficacy model is calibrated such as that the modified TiTE-CRM will eventually select a BCT duration associated with 75%-85% successful PA success, i.e., within 5 percentage points of our target [30]. The sample size (n=42) is determined to achieve 60% probability of correct selection (PCS) under logistic dose-efficacy curves with slope = 0.69 (i.e., an OR = 2) [31]. As this is small-scale pilot study, power and sample size will be calculated solely for the primary aim.

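### The MED requires success in 80% or more, but the design is calibrated to select a duration anywhere from 75% to 85%, and the 60% probability of correct selection is quoted without saying what counts as correct

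*Combined protocol and SAP*

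**What the plan says.** Section 4 sets the primary aim as the MED of the intervention "required to increase PA by an average of 2,000 steps per day between run-in and follow-up periods in at least 80% of participants". Section 12 adds minimality: "The minimum effective dose (MED) will be defined as the smallest BCT dose duration associated with a successful PA increase", again with a floor of 80% of participants. Section 12 also says that, once enrolment is complete, the team will identify the duration at which 80% or more reach the goal. The summary in Section 2 words the MED slightly differently, tying the smallest duration to 80% with no floor.

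On estimation, Section 12 says: "The MED will be estimated based on the modified TiTE-CRM, which is an adaptive model-based, dose-finding design for estimating the maximum tolerated dose". It then adds: "In this study, we will adapt the TiTE-CRM for the purpose of MED estimation". The adaptation is not described further.

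For dosing between cohorts, Section 9 says durations are set "based on the updated MED estimate according to the modified TiTE-CRM model and data from the previously enrolled participants". Section 11 points to the responder proportion in the preceding cohort: "The treatment response for the prior cohort will be used to guide the dose administered to the subsequent cohort using modified TiTE-CRM methodology".

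The sample-size paragraph of Section 12 states that the model is calibrated so that the method will "eventually select a BCT duration associated with 75%-85% successful PA success, i.e., within 5 percentage points of our target". It continues: "The sample size (n=42) is determined to achieve 60% probability of correct selection (PCS) under logistic dose-efficacy curves with slope = 0.69", which it equates to an odds ratio of 2. It does not define correct selection or say where on those curves the MED lies.

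**The concern.** The definition has a floor at 80%. The calibration has a band centred on 80%, and its lower half lies below that floor. Two selection rules are compatible with different parts of the text:

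- **Literal rule:** the smallest duration whose model-estimated success is 80% or more. This follows the definition and the closing identification sentence of Section 12.
- **Closest rule:** the duration whose estimated success is nearest 80%. This fits the two-sided band.

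The trial's main output is a single number of weeks, and the two rules can name different weeks from the same data. Under the closest rule, the reported duration may not support a claim that at least 80% succeed. Under the literal rule, the quoted PCS may be more favourable than the design delivers. If the rule is still open when the data are in, it can be chosen after the result is seen.

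**Working it through.** **1. Inputs from the plan.** Durations of 1 to 10 weeks, start at 5 weeks, 14 cohorts of 3 (14 × 3 = 42), target 80%, half-width 5 points, logistic slope 0.69 (exp(0.69) ≈ 2), PCS 60%.

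**2. Assumptions, not in the documents.** The odds ratio of 2 applies per week. The working model is a one-parameter CRM (power or logistic) on the failure scale, target 20%. Prior variance was about 1.34 in the main runs and was varied in others. All outcomes are complete, with no time-to-event weighting.

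**3. Where band and definition part company.** With OR 2 per week, the odds of success double each week. An 80% duration has odds 4, so its neighbours have odds 2 (66.7%) and 8 (88.9%). The defined MED therefore has odds from 4 up to 8, and the next shorter duration has half that.

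- MED odds 4 to 5.67 (80%–85%): the next shorter duration is at 66.7%–73.9%. Only the MED is in the band, so both criteria name the same duration.
- MED odds 5.67 to 6 (85%–85.7%): neither duration is in the band.
- MED odds 6 to 8 (85.7%–88.9%): the next shorter duration has odds 3 to 4 (75%–80%). The only duration in the band is one that fails the definition.

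On the log-odds scale the third zone is ln(8/6)/ln 2 = 0.288/0.693 = 42% of possible positions.

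**4. Reproducing the 60%.** True curve: logit p(k) = logit p(MED) + ln 2 × (k − MED week). With the MED exactly at 80%, the closest rule selects it in about 58%–65% of simulated trials, so 60% is reproduced. At OR 1.5 and 3 per week the average is 40% and 73%, so of these values only 2 per week matches.

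**5. Both rules on the same curves, n = 42.** Ranges run over MED weeks, working models and priors.

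| True success at MED | Next shorter | MED selected: literal | MED selected: closest | Selected duration truly below 80%: literal | closest |
|---|---|---|---|---|---|
| 80% | 66.7% | about 40%–48% | about 58%–65% | 3%–5% | 13%–17% |
| about 82% | about 70% | 46%–56% | 59%–62% | 7%–9% | 20%–26% |
| 85% | 73.9% | 55%–60% | 48%–55% | 16%–21% | 38%–45% |
| 87.6% | 78% | 50%–54% | 30%–36% | 31%–39% | 60%–68% |

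**6. Reading the table.** For the literal rule, 60% is roughly its best case, reached with the MED near 84%–86%. For the closest rule, 60% holds with the MED at or just above 80%, and the share of selections truly below 80% rises as the next shorter duration approaches 80%.

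**The case against.** Several points on the other side are fair.

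- **The plan is not silent on the final step.** The closing identification sentence of Section 12, read with its definition and named estimator, most naturally means the literal rule. That stands. It still does not say whether the 80% is a model estimate, an observed proportion or a posterior probability, or what is reported if no duration qualifies.
- **The band is a calibration property.** A reader might infer that the plan holds two rival definitions of the MED. The text does not go that far. The defect is that the calibration tolerates durations the definition rejects, with no rule linking the two.
- **The PCS does not identify the rule.** A reader might infer from the match in step 4 that the sponsor used closest-to-80%, or that n = 42 is wrong. Neither follows. The curve positions are not given, and the literal rule also comes close to 60% with the MED near 85%; in single settings it reached 64%. Averaged over MED positions from 80% to 88% in 1-point steps (power model), the closest rule found the defined MED in 51% and the literal rule in 52%.
- **Exactly 80% is a knife-edge.** There a point-estimate threshold misses about half the time at any size: 41%–45%, 45%–49% and 44%–51% at n = 42, 150 and 600. That part of the gap is not a sample-size fault.
- **Cited methods.** The calibration and the PCS each cite a methodological paper. Those papers are not available here and may define correct selection. The plan itself should do so.
- **Pilot status.** Section 12 calls the result preliminary. This lowers the stakes, but one duration remains the primary output.

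**Conclusion.** The point holds as an inconsistency in the text: a one-sided definition at 80%, a two-sided calibration at 75%–85%, and a PCS with no stated meaning of correct. It should be fixed before the final analysis.

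The practical difference lies mainly in how often the selected duration is truly below 80%. Averaged over the MED positions from 80% to 88%, this is about 38% under the closest rule against 17% under the literal rule. The literal rule reaches 60% only near its best case.

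Confidence in the textual conflict is high. Confidence in the numbers is moderate, because the working model, the prior, the unit of the odds ratio and the MED position are all assumed, and the time-to-event weighting was left out.

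**What to change.** State one final selection rule, applied after all follow-up is complete, and reconcile Sections 2, 4, 11 and 12 with it. The choice is the sponsor's:

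- **(a)** Select the smallest duration with model-estimated success of 80% or more, as Section 12 implies. Define correct selection as naming that MED, and restate the PCS over stated curve positions. Report that no MED was found within 1–10 weeks if no estimate reaches 80%. *Cost:* a less favourable PCS, about 40%–60% over the positions above. The no-MED report can also be wrong: if 10 weeks is truly at exactly 80%, in 17%–54% of simulated trials; if 80% is reached at 8 weeks, in at most 4%.
- **(b)** Keep closest-to-80%, state the curves for which the 60% PCS holds, and reword the aim and conclusion as the duration estimated closest to 80%. *Cost:* a weaker claim. Against its own target the PCS also falls, to about 44%–55% with the MED at 85%–86%.

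Optional additions are a prespecified margin under (b), such as the plan's own 75%, below which no duration is named, and an interval for estimated success at the selected duration. Even under (a), a point estimate of 80% or more does not show that true success is at least 80%.

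The work is a few sentences and a simulation re-run. No change to enrolment or data collection is needed.

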### 13. SPECIMEN BANKING

- *If specimens will be banked for future research, describe where the specimens will be stored, how long they will be stored, how they will be accessed and who will have access to the specimens*
- *List the information that will be stored with each specimen, including how specimens are labeled/coded*
- *Describe the procedures to release the specimens, including: the process to request release, approvals required for release, who can obtain the specimens, and the information to be provided with the specimens.*

N/A

### 14. DATA MANAGEMENT AND CONFIDENTIALITY

- *Describe the data and specimens to be sent out or received. As applicable, describe:*
  - *What information will be included in that data or associated with the specimens?*
  - *Where and how data and specimens will be stored?*
  - *How long the data will be stored?*
  - *Who will have access to the data?*
  - *Who is responsible for receipt or transmission of data and specimens?*
- *Describe the steps that will be taken to secure the data during storage, use and transmission.*

Fitbit

This pilot study uses commercially available, non-NFC, Fitbit devices to remotely monitor participant activity. All enrolled participants will be provided with a study account that has been created by the research team with no identifying information to the participant. The email address of the study account contains a unique identifier

(e.g. northwellf25). Data collected will include daily steps, floors climbed, activity intensity, sleep duration, battery life, last sync, and estimated minutes in sleep stages. A file linking the Fitbit identifier to the study participant will be housed in a Northwell-approved drive to store PHI, and be accessible only by members of the study team listed in the IRB application. Coded data from Fitbit will remain stored in a Northwell-approved drive indefinitely.

#### Fitabase

This pilot study will use Fitabase to retrieve Fitbit data from participants. Fitabase is a secure, online portal. The Fitbit study account provided to the participants will be linked to an identification number in the Fitabase system (e.g. FLT01). No information that could be used to identify a participant will be stored on Fitabase. Only the research team will have access to data that will be able to connect a research participant to their Fitabase ID. Data collected will include last sync date, battery charge status, daily steps, floors climbed, activity intensity, sleep duration, and estimated minutes in sleep stages. Fitabase will stop tracking participant data at the trial end date selected by the research coordinator. As an added measure, participants will be instructed to remove the Fitbit study account from their device if they plan on keeping the Fitbit.

#### Medication Adherence

We will monitor daily adherence to clinically prescribed statins using the eCAP smart pill bottle by Information Mediation Corporation. eCAP smart pill bottles are a type of medication adherence tracking device. The eCAP is an electronic content monitor (ECM) that tracks medication usage without active participant input and without the use of any downloadable app. While the eCAP ECM system does have the capability to integrate with android or iOs phones, the study team will not utilize this feature. eCAP stores information about the opening of the pill bottle but no patient information or identifying data is stored on the device. Compliance data will be available for download by the study team upon receipt of the eCAP smart pill bottle at the end of the research.

#### Eligibility, Consent, and Survey and Fitbit Data

Survey and Fitbit data will be collected and stored using RedCap, which is a Northwell security-review approved system for collecting and storing research data, including PHI. The study team will have access to all data, including PHI, throughout the study. Pooled results will be used to assess gaps in phenotypic understanding to empirically determine if modeling precise therapy is feasible.

The study team takes data confidentiality very seriously. Data collected for this research will be maintained on a HIPAA-compliant Northwell-approved SQL database. All members of the research team with access to identifiable and coded data will be trained and included on the IRB submission for approval. Regular meetings will take place with the PI and other members of the study team to ensure protocol adherence and data accuracy. Data collected for this study will be maintained in its original and unaltered source data state in a Northwell-approved SQL database on a Northwell-approved drive to store PHI indefinitely. Data collected under this research may be used for future research in coded format without additional consent as per the consent form participants sign and with appropriate IRB approval as required. Any additional data that must be shared will be done so

according to the consent form participants signed. Only research staff listed within this IRB submission will have access to identifiable information. Anonymized data may be stored indefinitely for reference following the conclusion of the study. The participant will be made aware of all data collected in the consenting process.

This research is funded by the NIH, thus a Certificate of Confidentiality has been issued for this research. Certificates of Confidentiality (CoCs) protect the privacy of research subjects by prohibiting disclosure of identifiable, sensitive research information to anyone not connected to the research except when the subject consents or in a few other specific situations.

## 15. DATA AND SAFETY MONITORING PLAN

*A specific data and safety monitoring plan is only required for greater than minimal risk research. For guidance on creating this plan, please see the [Guidance Document on the HRPP website](#).*

*Part I – this part should be completed for all studies that require a DSMP.*

*Part II – This part should be completed when your study needs a Data and Safety Monitoring Board or Committee (DSMB/C) as part of your Data and Safety Monitoring Plan.*

### Part I: Elements of the Data and Safety Monitoring Plan

- *Indicate who will perform the data and safety monitoring for this study.*
- *Justify your choice of monitor, in terms of assessed risk to the research subject's health and well being. In studies where the monitor is independent of the study staff, indicate the individual's credentials, relationship to the PI, and rationale for selection*
- *List the specific items that will be monitored for safety (e.g. adverse events, protocol compliance, etc)*
- *Indicate the frequency at which accumulated safety and data information (items listed in # above) will be reviewed by the monitor (s) or the DSMB/C.*
- *Where applicable, describe rules which will guide interruption or alteration of the study design.*
- *Where applicable, indicate dose selection procedures that will be used to minimize toxicity.*
- *Should a temporary or permanent suspension of your study occur, in addition to the IRB, indicate to whom will you report the occurrence.*

Given that study activities involve no more than risks encountered in daily life (increased time spent walking by healthy, working individuals), the study has received approval from the NIA for a safety monitor. [name] has been approved to provide safety monitoring for this pilot. [name] is a family medicine clinician and oversees Northwell's Health Solutions programs.

